Troponin (0 und 3 h)	X			
Clinical chemistry	X			
DZHK-Biobanking (optional)		X		
Study-specific examinations				
GRACE-Score	X			
Adverse Events	X	X	X	X
ECG	X	X		
Echocardiography (TTE)		X		
Coronary angiography		X		
endpoints				
Acute coronary syndrome (ACS)		X		
Recurrent cerebral ischemia, myocardial infarction, mortality		X	X	X

Table 1: PRAISE study procedures

Statistical analysis:

Sample size calculation:

The sample size calculation of the PRAISE study is based on data from the TRELAS study (Troponin elevation in acute stroke)⁹. In the TRELAS study, 7/29 (24%) of ischemic stroke patients with troponin elevation had a coronary culprit lesion and 11/29 (38%) of patients had dynamic troponin elevation (i.e. Δ change $> 50\%$). Of 11 patients with dynamic troponin elevation, 6 patients (54%) had a coronary culprit lesion. In patients without dynamic troponin elevation, only one patient (1/18=6%) had a coronary culprit lesion. Thus, the odds ratio of a dynamic troponin elevation for presence of a coronary culprit lesion was at 20.4. Due to the small sample size of the TRELAS study, we used the lower limit of the 80% confidence interval of the odds ratio (~4) to calculate the sample size for the PRAISE study. We assumed that the proportion of stroke patients with dynamic troponin elevation will be similar to the TRELAS study. Thus, 203 patients will have to be included to achieve a statistically significant result with a power of 80% (alpha=0.05). Since the TRELAS study only recruited patients with an initial hs-troponin T value > 50 ng/l (Roche Elecsys Assay), the proportion of patients with dynamic troponin elevation will likely be even higher in PRAISE. In order to compensate for cases of withdrawal of consent we plan to include 251 patients. The primary hypothesis will be tested using an intention-to-diagnose analysis by calculation of the odds ratio of acute coronary syndrome in patients with dynamic vs. stable troponin elevation. Secondary endpoints will be analyzed using the same statistical method.

In order to assess other predictors of acute coronary syndrome we will use the Chi-Square-test for dichotomous variables and the Wilcoxon-Test for continuous variables.

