In addition, we will perform univariable analyses and multivariable logistic regression analyses to calculate unadjusted and adjusted odds ratios for acute coronary syndrome. We will take a number of baseline regressors into account including age, sex, GRACE-Score, history of coronary heart disease, atrial fibrillation, heart failure, wall motion abnormalities on echocardiography and ACS-typical changes on ECG.

In an exploratory analysis, we will calculate an optimized multivariable logistic regression model using backward selection. In addition, we plan to calculate the best cut-off of troponin levels to predict acute coronary syndrome using the maximum area under the receiver operating characteristic (ROC) curve. Subgroup analyses will be defined in the statistical analysis plan before the first endpoint analysis is performed.

Interim analyses

In order to assess safety of the study, we will perform an interim analysis of the occurrence of serious adverse events of special interest (SAESI, see below) after inclusion of 100 and 200 patients, respectively. This analysis will be used by the DSMB to consult the Steering Committee concerning the continuation or premature termination of the study due to safety concerns.

Methods against bias

PRAISE is a multicenter observational study. Recruiting sites are stroke centers in Germany. The diagnosis of “acute ischemic stroke” will be established by experienced neurologists. ECG, echocardiography and coronary angiography will be performed by experienced cardiologists according to SOPs. All study examinations will be re-assessed by blinded core laboratories (see above). Since troponin will be measured by the recruiting study sites before study inclusion using different assays, troponin will also be re-measured at a core laboratory ([name], UKE Hamburg) using the same biosamples. The primary endpoint will be adjudicated by an independent endpoint adjudication committee, which will be blinded to patients’ troponin levels. The assessment of functional and cognitive outcome will be performed using standardized scores (see above).

The primary hypothesis that has been described in this protocol will be tested in an intention-to-diagnose analysis in order to prevent possible selection bias. A per-protocol-analysis is planned as a secondary analysis.

[figure not shown]
Study timeline:

Fig. 1: study timeline

Ethical considerations:

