2.3 Sample size

To be assessed for eligibility (n = 8,750 patients with ischemic stroke, thereof n = 1,250 with troponin elevation according to the inclusion criteria)

To be allocated to trial (n = 251)

To be analyzed (n = 203)

Full details of sample size calculation can be found in the study protocol.

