5.3.2 Adjusted analyses

For the primary endpoint univariate and multiple logistic regression models will be fitted to the data to calculate unadjusted and adjusted odds ratios, including a series of baseline regressors:

- Age (continuous)
- Gender (dichotomous)
- Diabetes (dichotomous)
- Dyslipidemia (dichotomous)
- Renal failure (eGFR < 60 ml/min dichotomous)
- History of CHD (dichotomous)
- History of heart failure (dichotomous)
- History of atrial fibrillation/flutter (dichotomous)
- Haemoglobin (<12 g/dl for women, < 13 g/dl for men, dichotomous)
- Initial NIHSS (continuous)
- Heart rate (> 100/min, dichotomous)
- ECHO core lab: wall motion disturbance (dichotomous)
- ECG core lab findings: ACS typical changes (dichotomous)
- Peak troponin T value (continuous)

In an explorative analysis, an optimized multiple logistic regression model for the prediction of the primary endpoint is derived using the following procedure: in the first step, a multiple logistic regression model is established in a blinded manner, i.e. without taking troponin values into account, including relevant confounding variables into the model. In order to decide which variables are included in the model, clinical and statistical criteria are used, considering the distribution of the variables and their structure of missing values.

In the second step, variable selection is performed using backward selection.

In the last step, an unblinded analysis is performed, i.e. the troponin is included in the prognosis model to predict the primary endpoint. The final choice of variable selection method is based on the technical feasibility of the model, use of performance parameters, and clinical considerations. For the calculation of the ROC-AUC as performance measure, a 10-fold validation procedure will be performed.

The same procedure is applied in order to derive a prognostic model for the prediction of the presence of type 1 myocardial infarction as well as in those patients in whom ACS is present, for the prediction of type 1 vs. type 2 myocardial infarction as adjudicated by the EAC.

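### SAP 5.3.2 leaves the variable selection method open in its unblinded step, with performance as one criterion and no protection of the reported 10-fold AUC, so that AUC may be too high

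*SAP*

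**What the plan says.** SAP section 5.3.2 (Adjusted analyses) derives the model in three steps. The first builds a logistic model without troponin. The second reads: "In the second step, variable selection is performed using backward selection". The last adds troponin in an unblinded analysis. The protocol names the same method under Statistical analysis: "we will calculate an optimized multivariable logistic regression model using backward selection".

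The paragraph on the unblinded step goes on: "The final choice of variable selection method is based on the technical feasibility of the model, use of performance parameters, and clinical considerations". The sentence after it reads: "For the calculation of the ROC-AUC as performance measure, a 10-fold validation procedure will be performed". SAP 5.3.3 then looks for the algorithm with the highest AUC.

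The SAP lists no candidate selection methods, no stopping criterion for backward selection and no rule for weighing the three criteria. It does not say whether selection is repeated within the folds. No nested loop, bootstrap correction or external validation is planned. The same procedure is to be used for type 1 myocardial infarction and, among patients with ACS, for type 1 against type 2.

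The model building is called explorative in SAP 5.3.2. SAP 1.1 and 1.2 nevertheless give development of the diagnostic algorithm as the study's primary goal.

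**The concern.** A method that two places name is reopened in the paragraph that describes the unblinded analysis, and performance is one of the grounds for choosing. Cross-validation corrects only for steps that are repeated inside the folds. If several methods are run, the one with the best cross-validated AUC is kept, and that same AUC is reported, the figure is a maximum of several noisy estimates. It is then no longer an estimate of how the chosen model will perform in new patients.

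The same reasoning applies one level down. If backward selection is run once on all patients and only the coefficients are refitted in each fold, the held-out patients have already helped to choose the variables.

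Readers will judge the algorithm largely by this AUC. An inflated value would make it look more ready for use than it is.

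**Working it through.** **Inputs from the documents.** SAP 2.3 gives "To be analyzed (n = 203") out of "To be allocated to trial (n = 251"). The protocol's sample size section gives "7/29 (24%) of ischemic stroke patients with troponin elevation had a coronary culprit lesion", used here as a stand-in for ACS, and "11/29 (38%) of patients had dynamic troponin elevation". It also gives 6% events in stable patients and a design odds ratio of about 4. SAP 5.3.2 lists 14 regressors, peak troponin T included.

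**The plan's own figure.** An odds ratio of 4 applied to 6% gives odds of 4 × 0.06/0.94 = 0.2553, so p2 = 0.2553/1.2553 = 0.2034. With k = 11/18 = 0.611, the pooled proportion is (0.06 + 0.611 × 0.2034)/1.611 = 0.1144. The two-proportion formula is

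n1 = [1.96·√((1 + 1/k)·p̄(1 − p̄)) + 0.842·√(p1(1 − p1) + p2(1 − p2)/k)]² / (p2 − p1)² = 108.0.

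The continuity correction, (n1/4)·[1 + √(1 + 2(1 + 1/k)/(n1(p2 − p1)))]², gives 125.7, hence 126 stable and 0.611 × 125.7 = 76.8, hence 77 dynamic patients. The total is 203, as stated. 203/(1 − 0.19) = 250.6 gives 251. The documents state no AUC, no target AUC and no number of methods, so the bias itself has no stated figure to reproduce.

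**Information available.** 203 × 7/29 = 49 events, about 5 per fold and 49/14 = 3.5 per candidate variable.

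**Simulation.** 600 data sets per scenario; n = 203, 24% events, 14 predictors, logistic models, stratified 10-fold AUC; true AUC from 20,000 new patients. Assumed, not in the documents: effect sizes, predictor prevalences and the sets of methods.
- Three methods: backward p < 0.05, backward p < 0.157, univariable screening p < 0.20.
- Six methods: these plus backward p < 0.10 with troponin forced in, the full model, and ridge.

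The method with the highest 10-fold AUC is kept. Bias = reported 10-fold AUC minus true AUC (standard error 0.002 for the best-of-several columns):

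| Signal (true AUC) | Fixed backward p < 0.05, selection in folds | Best of 3, in folds | Best of 6, in folds | Fixed backward p < 0.05, selected once on all data | Best of 3, selected once |
|---|---|---|---|---|---|
| None (0.50) | 0.000 | +0.030 | +0.048 | +0.051 | +0.106 |
| Weak (about 0.64) | −0.006 | +0.014 | +0.024 | +0.064 | +0.066 |
| Moderate (about 0.75) | −0.007 | +0.009 | +0.013 | +0.036 | +0.039 |

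For example, best of three in folds at moderate signal: 0.765 − 0.756 = 0.009.

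**Second simulation, different assumptions.** 400 data sets, 15 predictors of which 4 informative, selection in folds. At 24% ACS the bias was +0.017 (best of three) and 0.660 − 0.631 = +0.029 (best of six). The second scenario used 11.4% ACS, which follows from the design figures: 0.06 × 18/29 + 0.2034 × 11/29 = 0.114, or about 23 events in 203. There it was +0.025 and 0.652 − 0.609 = +0.043. With backward selection fixed, it was −0.003 and −0.009.

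**Scale.** The Hanley–McNeil standard error of an AUC is √{[A(1 − A) + (m − 1)(Q1 − A²) + (n − 1)(Q2 − A²)]/(mn)}, with Q1 = A/(2 − A) and Q2 = 2A²/(1 + A). With m = 49 and n = 154, A = 0.75 gives √(14.28/7546) = 0.044 and A = 0.63 gives √(17.04/7546) = 0.048.

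**The case against.** The SAP permits a best-of-several AUC; it does not prescribe one. Feasibility and clinical considerations count as well, performance parameters is plural and undefined, and nowhere is it said that several methods will be run or that the highest AUC decides. The highest-AUC aim in SAP 5.3.3 concerns the algorithm, not the selection method. A reader might infer that the reported AUC is bound to be inflated; the text does not support that.

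The sentence also does not say when the choice is made. It could summarise the whole procedure. A reader might infer that the blinded model building is undone, but nothing says the blinded variable set is rebuilt after troponin is added.

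The size is open to challenge too. The full model and ridge are not variable selection methods, so the best-of-three figures are closer to the wording. With a real signal at 24% events, the bias from the choice alone is below one standard error of the AUC.

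All of this stands, and it limits the certainty and size of the point. It does not remove it: the stated rule allows a choice informed by performance, AUC is the only measure named, and nothing planned would correct the reported value. An explorative label allows flexibility, but it does not turn a maximised AUC into an estimate of performance.

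**Conclusion.** The point holds as a risk that the SAP leaves open. If the 10-fold AUC guides the choice of method and is then reported, it may be too high by about 0.01 to 0.03 (best of three) or 0.01 to 0.05 (best of six) at n = 203, with the smaller values when the signal is stronger. These figures rest on assumed methods and effect sizes, and on culprit lesions standing in for ACS.

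The silence on repeating selection inside the folds can matter more. A single fixed backward procedure selected once on all data is too high by 0.036 to 0.064 with a real signal, and choosing among methods then adds almost nothing. Fixing the method alone is therefore not enough.

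A reader might infer that the main result is at risk. It is not: the primary diagnostic odds ratio in SAP 5.1.1 does not depend on this model. What is exposed is the performance figure for the algorithm. The type 1 against type 2 model uses ACS patients only (roughly 23 to 49 under the figures above), so the bias there is likely to be larger.

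**What to change.** Before unblinding, amend SAP 5.3.2 as follows.

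- State one selection method. Backward selection is already named in step two and in the protocol. Give one stopping criterion and a stated fallback if the model does not converge. Feasibility and clinical considerations can stay as grounds for which variables enter in step one.
- State that all data-driven selection is repeated inside every fold.
- If several methods are to be compared, list them beforehand, make the choice in an inner loop, and report only the outer-loop AUC. A bootstrap that repeats the whole process, choice of method included, with the optimism-corrected AUC reported, would serve as well.
- Apply the same rules to the type 1 and the type 1 against type 2 models.

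The cost is SAP wording and some extra computation. The downside is less freedom after unblinding and a slightly lower reported AUC.

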1.2 Objectives

The primary goal of the multicenter PRAISE study is to develop a diagnostic algorithm to better identify ACS as origin of troponin elevation in patients with an acute ischemic stroke. The primary hypothesis will test whether dynamic troponin levels (as compared to stable ones) indicate presence of ACS. The following hypotheses will be tested:

Primary hypothesis: A dynamic troponin elevation (>50% change at measurement after 3 hours) indicates an ACS in patients with an acute ischemic stroke. The change in troponin level (dynamic vs. stable after 3 hours) within patients with an acute ischemic stroke can be used to differentiate whether an ACS is present.

Endpoint: diagnosis of “ACS”, determined by an independent endpoint adjudication committee.

1. Secondary hypothesis: Stroke patients with dynamic troponin change have a worse functional outcome three or twelve months after the event in comparison to those with stable troponin.

Endpoints: Modified Rankin-Scale (mRS) after three and twelve months.

2. Secondary hypothesis: Stroke patients with dynamic troponin change have an increased risk for recurrence of cardiovascular events and a higher mortality rate in comparison to those with stable troponin.

Endpoints: Brain infarcts, transient ischemic attack (TIA), myocardial infarction (MI) and death as well as the combined endpoint thereof (MACE) during the acute inpatient stay, after three and twelve months.

In addition, in an exploratory approach we want to establish a combined rule-in/rule-out diagnostic algorithm to identify the subgroup of troponin-positive stroke patients in whom the diagnosis of ACS (i.e. type I vs. type II MI) vs. not is made by means of coronary angiography including stroke-specific cut-off values for troponin and other biomarkers, the value of ECG, echocardiography, clinical parameters, and combinations thereof.

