5.3 Additional analyses

The primary outcome analysis is repeated in the PP population. Additional analyses of the presence/absence of ACS in relation to presence/absence of dynamic troponin elevation include the calculation of further diagnostic accuracy measures like sensitivity and specificity together with the 95%-confidence interval.

A mediation analysis will be conducted to identify direct and indirect effects of the diagnostic group (dynamic vs. stable) and additionally peak troponin T in patients with available troponin T values (exposure variables) and the presence of ACS (yes vs. no) as well as presence of MI type 1 (yes vs. no) and in patients with ACS MI (Type 1 vs. Type 2) (mediator variables) on mortality and MACE (target outcome) using accelerated failure time models. This will be performed after unblinding of the diagnostic groups and analysed in an explorative manner.

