5.3.3 Prediction

We will calculate the area under the Receiver-Operating-Characteristic-Curves (ROC-analysis) to evaluate the predictive accuracy of changes in troponin alone, and adjusted for the variables found in the step above, particularly relative changes in the 20% to 50% interval, for the presence of ACS, the presence of type 1 myocardial infarction as well as in those patients in whom ACS is present, for the prediction of type 1 vs. type 2 myocardial infarction in stroke patients using Harrell's c statistic to determine the best cut-off to predict ACS as well as type 1 myocardial infarction.

We will calculate a prediction algorithm that identifies patients with ACS with highest area-under-the-curve (AUC) in a ROC-Curve (ROC-analysis of c-statistics) and which takes the results of pre-defined diagnostic procedures into account.

A gender-specific analysis will be conducted to determine if there are different cut-off values by testing an interaction between gender and troponin change.

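### The exploratory rule-in/rule-out algorithm is to be judged by ROC-AUC, with no calibration check and no shrinkage, so its low predicted ACS risks will tend to be too low and nothing planned would show it

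*SAP*

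**What the plan says.** SAP 1.2 sets the aim: "in an exploratory approach we want to establish a combined rule-in/rule-out diagnostic algorithm". Finding a diagnostic algorithm for ACS is also the stated primary goal of the study in the Protocol (Study aims) and in SAP 1.1 and 1.2.

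SAP 5.3.2 lists 14 regressors, peak troponin T among them. It then describes the derivation in three steps: a blinded model without troponin, whose variables are chosen on clinical and statistical grounds; then "In the second step, variable selection is performed using backward selection"; then the addition of troponin. No significance level for removal is given. On performance it says: "For the calculation of the ROC-AUC as performance measure, a 10-fold validation procedure will be performed". The final choice of selection method may also rest on "use of performance parameters, and clinical considerations", which are not named.

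SAP 5.3.3 gives the criterion for the algorithm: "We will calculate a prediction algorithm that identifies patients with ACS with highest area-under-the-curve (AUC) in a ROC-Curve". The Protocol (Statistical analysis) likewise plans backward selection and a troponin cut-off chosen by maximum area under the ROC curve.

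SAP 5.3 plans "further diagnostic accuracy measures like sensitivity and specificity together with the 95%-confidence interval", but for dynamic versus stable troponin, not for the multivariable algorithm. Neither document mentions a calibration slope, intercept or plot, shrinkage or penalised estimation, a predicted-risk threshold, or the ACS rate in a rule-out group.

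**The concern.** A rule-out statement is a statement about absolute risk: patients in this group have ACS with at most some small probability. AUC measures only whether patients with ACS are ranked above those without. If every log-odds is doubled, the AUC stays the same while low risks become much too low and high risks much too high.

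Backward selection on few events errs in this direction. Variables tend to survive when their estimated effect is by chance too large, and unpenalised coefficients are then carried into new patients. A sound cross-validated AUC could therefore stand beside predicted risks that understate ACS in the group called low risk. The Protocol (Background) explains that the tool should help clinicians decide in whom an invasive procedure is worthwhile, so understating risk at the low end is the unwelcome direction of error.

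**Working it through.** **Inputs from the documents.** N to be analysed is 203 (SAP 2.3). In the pilot study 7/29 (24%) had a culprit lesion, 11/29 (38%) were dynamic, the stable-group rate was 1/18 (rounded to 6%), and the planning odds ratio was about 4, with power 80% and alpha 0.05 (Protocol, Sample size calculation). Tests are two-sided (SAP 3.1). SAP 5.3.2 lists 14 regressors. The 24% is a culprit-lesion rate used here as a stand-in for the ACS rate.

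**Reproducing the plan's 203.** Stable p0 = 0.06, odds 0.06/0.94 = 0.0638. Times 4 = 0.2553, so dynamic p1 = 0.2553/1.2553 = 0.2034. Ratio stable:dynamic r = 0.62/0.38 = 1.632. Pooled p̄ = (0.2034 + 1.632 × 0.06)/2.632 = 0.1145.

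n(dynamic) = [1.96·√((r+1)·p̄(1−p̄)) + 0.842·√(r·p1(1−p1) + p0(1−p0))]² / [r·(p1−p0)²] = 66.1, that is 67 + 110 = 177 in total. With the continuity correction, (n/4)·[1 + √(1 + 2(r+1)/(n·r·(p1−p0)))]² = 76.9, that is 77 + 126 = **203**. The stated figure is matched.

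**Events available.**
- At 24%: 203 × 7/29 = 49 events; 49/14 = 3.5 per listed regressor.
- At the rate implied by the inputs that give 203: 203 × 0.1145 = 23 events; 23.2/14 = 1.7 per regressor.

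**Simulation, set A** (150 to 200 studies per cell, N = 203, the 14 regressors plus dynamic troponin, evaluated on 20,000 new patients of known risk). Backward selection was applied to the non-troponin variables, and troponin was then added. Assumptions not in the documents: independent predictors, their prevalences, the removal level (0.157 or 0.05), no clinical pre-selection, and three strengths of true signal (AUC about 0.67, 0.74, 0.80). Ratios were taken before rounding.

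| ACS rate, true AUC | Removal p | Slope | Lowest tenth: predicted → true | Ratio | AUC: cross-validated / new patients |
|---|---|---|---|---|---|
| 24%, 0.67 | 0.157 | 0.65 | 7.5% → 14.5% | 1.95 | 0.62 / 0.65 |
| 24%, 0.67 | 0.05 | 0.76 | 9.6% → 14.3% | 1.49 | 0.62 / 0.66 |
| 24%, 0.74 | 0.157 | 0.66 | 5.2% → 10.5% | 2.03 | 0.65 / 0.70 |
| 24%, 0.74 | 0.05 | 0.74 | 7.1% → 11.4% | 1.60 | 0.68 / 0.69 |
| 24%, 0.80 | 0.157 | 0.74 | 2.5% → 4.6% | 1.83 | 0.74 / 0.77 |
| 24%, 0.80 | 0.05 | 0.78 | 2.9% → 4.4% | 1.52 | 0.75 / 0.77 |
| 11%, 0.74 | 0.157 | 0.57 | 1.7% → 4.3% | 2.57 | 0.66 / 0.68 |
| 11%, 0.74 | 0.05 | 0.60 | 2.3% → 4.7% | 2.03 | 0.66 / 0.68 |

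Cross-validated AUC was close to, or slightly below, the AUC in new patients in every row. The planned check would look sound while the slope was well below 1.

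**Hand check of the third row.** Take true log-odds ≈ average log-odds + slope × (predicted log-odds − average log-odds). With average 24% (−1.153), predicted 5.2% (−2.903) and slope 0.66: −1.153 + 0.66 × (−1.750) = −2.308, or 9.0%. That is 9.0/5.2 = 1.7 times the prediction, the same direction and order as the simulated 2.03.

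**Simulation, set B** (13 non-troponin candidates with backward selection, then dynamic status with odds ratio 4; 250 to 500 studies per cell, repeated under different assumed prevalences and weak odds ratios). Slopes were 0.65–0.73 at 24% and 0.54–0.64 at 11.4%. Ratios in the lowest tenth were about 1.4–2.1 and 1.5–3.3 respectively. Among patients predicted below 3%:
- 24% ACS: predicted 2.1–2.3%, true 9.1–9.6%, ratio 3.9–4.4; only about 1–4% of patients fall there.
- 11.4% ACS: predicted 1.7–1.9%, true 5.1–5.4%, ratio 2.7–3.4; about 18–26% of patients fall there.

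**With shrinkage.** Ridge regression with a cross-validated penalty, in the set A design, gave slopes of 1.03–1.07 and lowest-tenth ratios of 0.88–1.10 at 24% (1.11 and 0.91 at 11%).

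**The case against.** A reader might infer that patients called low risk would carry three to four times the ACS risk predicted. The documents do not support that. A ratio near 4 needs a cut at about 3% predicted risk. No document contains that cut-off or any other, and at 24% ACS that group was essentially empty in 44% to 79% of simulated studies, depending on the removal level. In the lowest-risk tenth at 24% a ratio of 3 or more occurred in only 8–32% of single studies.

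Other points against:
- The simulations skip the clinical pre-selection in SAP 5.3.2. With 7 retained candidates, assumed to include all the true predictors, the lowest-tenth ratio at 24% falls to 1.3–1.4. This stands and makes the figures above upper-side estimates if pre-selection is strict.
- The 11.4% rate is back-calculated. The documents state 24%, and SAP 1.1 about 25%. This stands; 24% is the main case.
- No published risk equation is promised, and uniform shrinkage does not change ranking. If the rule-out cut-off is set by observed sensitivity, shrinkage changes no classification. This stands and makes shrinkage conditional on predicted risks being reported or used.
- The SAP also refers to unnamed performance parameters, so AUC is the only named measure rather than the only permitted one. An unnamed measure commits the analysis to nothing.
- The work is labelled exploratory. That lowers the weight of the point, but the algorithm is still the study's stated primary goal.

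**Conclusion.** The point holds as a cheap improvement to an exploratory analysis. As written, the plan would yield predicted risks that are too extreme and has no step that would show it. Over the assumptions tried, the calibration slope is about 0.55 to 0.78. The lowest-risk tenth has about 1.5 to 2 times its predicted ACS risk at 24% ACS, and about 2 to 3 times at 11.4%. These sizes rest on independent predictors, assumed prevalences and odds ratios, assumed removal levels, and no clinical pre-selection. The direction follows from 1.7 to 3.5 events per listed regressor without shrinkage. The primary diagnostic odds ratio in SAP 5.1.1 is not touched.

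**What to change.** In SAP 5.3.2 and 5.3.3:
1. State that every selection step is repeated inside each resample, whether in the planned 10-fold validation or a bootstrap. The SAP does not say this now.
2. Report the optimism-corrected calibration slope and intercept, with a calibration plot, beside the AUC.
3. If predicted risks are reported or used to set a threshold, multiply the coefficients by the corrected slope and re-estimate the intercept, or fit by penalised regression (ridge or lasso).
4. Report the observed ACS rate (1 minus the negative predictive value) with its 95% CI in the rule-out group.

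The cost is SAP wording and modest computing; no new data, visits or patients are needed. The downside is that predicted risks become less extreme, so fewer patients will look eligible for rule-out.
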